1. INTRODUCTION AND BACKGROUND

1.1 Background

In 1945, Dr. H.D. Kesling envisioned that one day modern technology would enable the use of a series of tooth positioners to produce the kinds of movements required for comprehensive orthodontic treatment. Technology has made this vision a reality. Using advanced computer technology, Align Technology Inc. generates Invisalign®, a series of customized clear appliances, called "aligners." Each aligner is worn sequentially by the patient to produce extensive tooth movements in both upper and lower arches.

Class II malocclusions are often characterized by mandibular retrognathia and increased overjet. In patients with Class II malocclusions that are undergoing growth, appliances that reposition the mandible in a forward position can be used to correct class relationship.

Numerous clinical studies have demonstrated the effectiveness of such appliances in treating Class II malocclusions, as indicated by improved overjet, molar relationship, canine relationship, and/or orthopedic changes The aim of these appliances is to maintain the lower jaw in a forward position for as long as the appliances are worn, such that orthopedic and/or postural changes can take place to correct the patient's occlusion to a Class I by the end of the appliance treatment.

Most existing Class II appliances reposition the mandible in one step, such that the patient's jaw is positioned at the desired final position (or an overcorrected position) throughout the course of treatment. An alternative to this method is incremental repositioning, in which the total amount of A-P correction is divided into multiple steps. This method has been shown to be effective with the

and one advantage to this method is increased patient comfort especially at the start of therapy.

2. DESCRIPTION AND INDICATIONS FOR USE

2.1 Device Description

The Invisalign[®] System consists of a series of clear plastic aligners that are intended to replace conventional wire and bracket technology for many orthodontic cases. Each custom manufactured aligner exerts gentle, continuous forces to move teeth incrementally from their original state to a final, treated state. Each aligner is worn for about two weeks, then replaced by the next in the series until the final position is achieved. For years, orthodontists and dentists have used removable appliances for orthodontic treatment. Today, with the application of computer technology and custom manufacturing, Invisalign treats a broader range of cases with greater precision.

Mandibular Repositioning

Protocol Number: MRF-002

The Invisalign System with Mandibular Repositioning Feature (MRF) are removable devices that consist of an aligner with The upper and lower ramps are designed to interlock in such a manner that the mandible is held in a more protrusive position. The repositioning of the mandible can

be done sequentially in multiple increments (steps), in order to meet the doctor's treatment goal. The Invisalign System with MRF is made from the **Example 1**, a clear thermoplastic and utilizes current Invisalign System manufacturing processes.

2.2 Invisalign Intended Use

The Invisalign[®] System is indicated for the alignment of teeth during orthodontic treatment of malocclusion.

3. STUDY PURPOSE AND OBJECTIVES

3.1 Study Objectives

To demonstrate that growing teenagers which present up to full cusp Class II malocclusions can be treated using Invisalign with MRF. The primary objective of the study will be to demonstrate that Invisalign with MRF is not inferior to existing functional appliances to treat up to full cusp Class II malocclusions in growing teenagers. The objective will be met if Invisalign aligners with MRF correct Class II malocclusions at a rate that is not inferior to previously reported repositioning rates. This will be achieved if the median rate of correction using Invisalign with MRF at the end of mandible repositioning is non-inferior to published rates of movement (e.g. 0.42 mm/mo.

to a confidence level of 80%.

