4.1.2 Methods

Clinical and diagnostic methods to be used during this study are those which are routinely used in the diagnosis and treatment of malocclusions

each follow-up period as part of this study.

Inclusion Criteria:

A subject will be considered eligible if all of following inclusion criteria are fulfilled:

- Subject must have fully erupted dentition* excluding second premolars (5s), 2^{nd} and 3^{rd} molars
 - Age range 11-19 years old
- Subject that requires bilateral Class II correction and must require at least 3mm of correction as measured by first molar relationship

Exclusion Criteria:

A subject will be considered ineligible if any one of following exclusion criteria are fulfilled:

- Subject who has unerupted, erupting, partially erupted dentition (except unerupted second premolars with less than half root development, for 2nd and 3rd molars)
- Subject who has spaces between adjacent teeth larger than 3mm
- Subject with active caries
- Subject with periodontal disease
- Subject does not have at least 1st molar fully captured in PVS impression or intraoral scan.
- Subject with TMD symptoms
- Subject has undergone pre-treatment with any sagittal orthodontic appliance
- Subject has undergone pre-treatment with any orthodontic appliance 1 year prior to enrollment in the study
- Subject has known allergy to latex and plastic
- Subjects who are pregnant or will become pregnant during treatment

All subjects are free to withdraw from the study at any time without stating a reason or suffering from any disadvantage. In addition

Mandibular Repositioning

Feature (MRF)

Protocol Number: MRF-002

Group Assignment

Schedule of Study Visits

Screening

Subjects must be screened before enrollment in the study. Screening procedures by the investigator will include the following:

- 1. Perform a dental history exam
- 2. Review inclusion and exclusion criteria (Eligibility criteria)
- 3. Inform subject and obtain written informed consent

Initial Visit

Initial visit procedures and tasks will include the following:

Mandibular Repositioning

Protocol Number: MRF-002

8. Case Report Form: Enrollment Form

Aligner Delivery Visit

- 1. Deliver Aligners: Give the prescribed aligners to the subject and instruct them on how to wear the aligners with MRF features
- 2. Subject (QoL) Form: To be filled out by the subject.

3 Months After Start of Mandibular Advancement

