4.2 Number of Subjects/ Assignment to Treatment Groups

This study will enroll up to 165 patients. It is recommended that each site enroll a minimum of 10 subjects, to facilitate pooling of the data. It is recommended that each site recruits a minimum of 1 subject to have the occlusal feature set and a minimum of 1 subject

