6. DATA ANALYSIS

Data will be analysed by the Sponsor's statisticians or an identified consultant. The data will be analysed using standard univariate and bivariate techniques.

Significance will be demonstrated to a 80%

confidence level.

6.1 Primary endpoint analysis:

The primary objective of the study will be to demonstrate that Invisalign with MRF is not inferior to existing functional appliances to treat up to full cusp Class II malocclusions in growing teenagers. The objective will be met if Invisalign aligners with MRF correct Class II malocclusions at a rate that is not inferior to previously reported repositioning rates. This will be achieved if the median rate of correction using Invisalign with MRF at the end of the mandible repositioning is non-inferior to published rates of movement (0.42 mm/mo.

The secondary endpoints measured by

comparing the length of treatment

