6.2 Sample Size Calculation

[figure not shown]
The sample needed to demonstrate non-inferiority of the Invisalign with MRF to literature is found using a single sided proportion value, with the hypothesis that Ho P=Po and a 80% power is patients.

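### Does calling the 0.42 mm/month benchmark an example in section 3.1, but not in section 6.1, leave the primary comparison open?

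*Combined protocol and SAP*

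**What the plan says.** Section 3.1 (Study Objectives) says the objective is met if the device's "median rate of correction using Invisalign with MRF at the end of mandible repositioning" is "non-inferior to published rates of movement (e.g. 0.42 mm/mo". Section 6.1 (Primary endpoint analysis) repeats the criterion almost unchanged, with the benchmark written as "non-inferior to published rates of movement (0.42 mm/mo". The abbreviation before the number is the difference that matters here. In both sections the text stops just after the unit, where material has been removed.

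Both sections also describe the comparator in the plural: the device must correct "at a rate that is not inferior to previously reported repositioning rates". Section 6.2 says the sample size was "found using a single sided proportion value, with the hypothesis that Ho P=Po and a 80% power"; the resulting number of patients is not visible. Section 4.2 caps enrolment at 165 and adds: "It is recommended that each site enroll a minimum of 10 subjects, to facilitate pooling of the data".

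**The concern.** The study is non-randomized and no concurrent control group is visible, so the published rate is the comparator. If 0.42 mm/month is only an example, the comparator is not fixed in advance. A lower published rate makes non-inferiority easier to show and a higher one makes it harder, and either could be defended from the wording of 3.1 after the results are known. Section 6.1 appears to close that choice, so the two sections seem to give different decision rules for the primary claim.

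A second worry is attached to the first. Patients are pooled across sites, and the visible text says nothing about allowing for similarity of patients within a site. A confidence limit that ignores site could be too narrow.

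**Working it through.** **What can be reproduced.** The required sample size, the null and alternative proportions, the standard deviation (SD) and any margin are all out of view, so the plan has no figure on this point to recompute. What follows is a comparison of wording and an illustration of scale.

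**The two statements side by side.**

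| | Section 3.1 | Section 6.1 |
|---|---|---|
| Statistic | median rate at the end of repositioning | the same |
| Benchmark | 0.42 mm/month, given as an example | 0.42 mm/month, no qualifier |
| Comparator wording | plural, previously published rates | the same |
| Rest of the parenthesis | removed | removed |

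There is one number, not two. Section 6.2 does not help either way: its null hypothesis concerns a proportion, not a rate in mm/month.

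**What a switch of benchmark would do.** Assumptions: normally distributed rates; SD 0.1, 0.2 or 0.3 mm/month; the same margin whichever benchmark is used; 165 analysed (the enrolment cap) or 80 (assumed); a distribution-free lower limit for the median at nominal one-sided 10%, the lower end of a two-sided 80% interval.

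The lower limit is the k-th smallest rate, with k the largest value for which P(Bin(n, 0.5) ≤ k − 1) ≤ 0.10.

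- n = 165: k = 74, exact error 0.080.
- n = 80: k = 34, exact error 0.073.

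Let the true median lie exactly at the pass limit built on 0.42. If the benchmark is lowered by d, the chance of false success is P(Bin(n, Φ(−d/SD)) ≤ k − 1). For d = 0.02 and SD 0.2, Φ(−0.1) = 0.460 and P(Bin(165, 0.460) ≤ 73) = 0.353. The full set is:

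| Benchmark used | n | SD 0.1 | SD 0.2 | SD 0.3 |
|---|---|---|---|---|
| 0.42 | 165 | 0.080 | 0.080 | 0.080 |
| 0.40 | 165 | 0.741 | 0.353 | 0.236 |
| 0.42 | 80 | 0.073 | 0.073 | 0.073 |
| 0.40 | 80 | 0.488 | 0.229 | 0.164 |

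If the 80% level is read as one-sided 20% (k = 77 at n = 165, exact error 0.175), the 0.40 figures at n = 165 become 0.868, 0.536 and 0.401. In the other direction, a benchmark 0.02 higher cuts 80% power at n = 165 (one-sided 10%) to 0.114, 0.428 or 0.564.

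The rows for 0.42 carry the conclusion: if the number in both sections is the one used, the error stays at or below nominal, whatever the SD.

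**Clinical scale of the assumed shift.** Section 4.1.2 admits a subject who "must require at least 3mm of correction as measured by first molar relationship". At 0.42 mm/month, 3 mm takes 3/0.42 = 7.14 months; at 0.40 it takes 3/0.40 = 7.50 months. The difference is 0.36 month, about 11 days.

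**Site.** With 16 sites of 10 (the number of sites is assumed), simulation of a limit that ignores site, at nominal one-sided 10%, gives error of about 9%, 9%, 12% and 14% at intraclass correlation (ICC) 0, 0.01, 0.05 and 0.10. With 16 uneven sites of 2 to 40 patients it is 8%, 9%, 14% and 18%. At nominal one-sided 20% with 16 sites of 10 it is 19%, 20%, 22% and 25%. Any excess depends on an ICC for which the document gives no source.

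**The case for a change.** The strongest case for a change is that both sentences define when the primary objective is met, that no visible text says which section governs, and that the mismatch remains whatever the removed text says. With an external comparator, choosing the rate is choosing the control. A difference of about 11 days in treatment time could decide the trial, and the repair is one deleted abbreviation and one added sentence.

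It stands that the wording differs and that one fixed reference is better practice. Under its assumptions the arithmetic is also right, on either reading of the 80% level.

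The inference that the benchmark is open does not stand. It needs a second rate, and none is visible. It also needs 6.1 to hold a single value where 3.1 does not, and the removed remainder of either parenthesis prevents that from being shown: 6.1 uses the plural as well and could list further rates.

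An added sentence could do harm. Declaring 0.42 the only benchmark might contradict text out of view. Calling it a performance goal could be read as setting the non-inferiority margin to zero, which would be a different hypothesis.

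The site analysis does not follow from the wording difference. Multi-site pooling makes it a reasonable thing to look at, but as a sensitivity analysis it would leave the primary decision untouched.

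**Conclusion.** This is a clerical difference between an objectives statement and the analysis section that carries it out. The natural reading is that 6.1 governs, that 0.42 mm/month is the reference rate, and that any margin applies to it. On that reading there is no excess error. Dropping the abbreviation from 3.1 would tidy the text without altering any result.

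The figures of 24% to 74% at 165 patients (16% to 49% at 80) describe a switch to a benchmark 0.02 mm/month lower. They depend on an assumed SD, an assumed second rate and an assumed change of comparator after the data are seen, so they measure what a departure from 6.1 could do and not a defect in the plan. The site figures rest on an assumed number of sites and an unsourced ICC, and give no ground for a change on this point.

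The conclusion would differ only if the removed text in 6.1 named several rates with no rule for choosing among them. The public document cannot show that either way.

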6 ALIGN CONFIDENTIAL

Protocol Number: MRF-002

	The secondary endpoints will be measured by
comparing length of treatment	
Both subject and doctor per	pention will be assessed

Both subject and doctor perception will be assessed.

All statistical comparisons will be conducted to an 80% confidence level.

3.2 Definitions

Term or Abbreviation	Definition	
AE	Adverse event	
A-P	Type of anterior-posterior orthodontic malocclusion treatment correction	
Buccal	Surfaces of crowns of teeth that face away from the tongue (toward the lips or toward the cheek)	
Class II Malocclusion	A type of orthodontic malocclusion	
CRF	Case Report Form	
FDA	Food and Drug Administration	
IRB	Institutional Review Board	
Investigator	The person responsible for the conduction of this study at each individual site. This will be the treating orthodontist. The term "Investigator" is used synonymously in this Protocol with "Principle Investigator", "Orthodontist" and "Doctor".	

Mandibular Repositioning

Feature (MRF)

Protocol Number: MRF-002

ΙΟ	Intraoral scans	
IPR	Interproximal Reduction	
OPG	Panoramic radiograph	
PVS	An orthodontic impression material (polyvinyl siloxane material)	
SAE	Serious adverse event	
Sponsor	Align Technology, Inc.	
Study Monitor or Clinical Research Associate (CRA)	Person from the Sponsor who monitors the study data for completeness, accuracy through on site visits, remote monitoring, etc.	
TMD	Temporomandibular joint dysfunction	
MRF	Mandibular Repositioning Feature	
SOP	Standard Operating Procedure	

Mandibular Repositioning

Protocol Number: MRF-002

4. STUDY DESIGN

4.1 Overview of Study Design

This study is a prospective, non-randomized Investigational Device Exemption study. It is designed to measure how safely and effectively Class II malocclusions are corrected in teenagers by repositioning the mandible. It will also examine how efficiently the repositioning will occur.

During the course of treatment, Investigators will monitor the use of the MRF in subjects and complete case report forms. Monitoring of the cases and completion of the case report forms will continue throughout the treatment of the Class II to Class I correction as well as through to the subject's end of Invisalign treatment or withdrawal from the study. Data from this correction will be analyzed and may be used for publication or regulatory purposes. After the use of the Invisalign aligners with MRF portion of treatment is completed, the subject will continue with their Invisalign treatment through to the end of treatment for the final study visit.

This data collection will coincide with the 3 and 6 month follow-up periods of the IDE clinical study. The data collected will be similar to that obtained at follow up visits.

All study subjects will be treated with Invisalign aligners that have been modified to meet the study requirements. All sites will be monitored by the Sponsor in accordance to the monitoring plan. All data collected will be analyzed by the Sponsor or a designated statistician.

All participating Investigators and designated office coordinators will be trained on the clinical study protocol and good clinical practices (GCP) by representatives of the Sponsor.

4.1.1 Materials

The cases will be submitted and fabricated at Align Technology, Inc.

Mandibular Repositioning

Investigators will also complete case report forms at

Feature (MRF)

Protocol Number: MRF-002

4.1.2 Methods

Clinical and diagnostic methods to be used during this study are those which are routinely used in the diagnosis and treatment of malocclusions

each follow-up period as part of this study.

Inclusion Criteria:

A subject will be considered eligible if all of following inclusion criteria are fulfilled:

- Subject must have fully erupted dentition* excluding second premolars (5s), 2^{nd} and 3^{rd} molars
 - Age range 11-19 years old
- Subject that requires bilateral Class II correction and must require at least 3mm of correction as measured by first molar relationship

Exclusion Criteria:

A subject will be considered ineligible if any one of following exclusion criteria are fulfilled:

- Subject who has unerupted, erupting, partially erupted dentition (except unerupted second premolars with less than half root development, for 2nd and 3rd molars)
- Subject who has spaces between adjacent teeth larger than 3mm
- Subject with active caries
- Subject with periodontal disease
- Subject does not have at least 1st molar fully captured in PVS impression or intraoral scan.
- Subject with TMD symptoms
- Subject has undergone pre-treatment with any sagittal orthodontic appliance
- Subject has undergone pre-treatment with any orthodontic appliance 1 year prior to enrollment in the study
- Subject has known allergy to latex and plastic
- Subjects who are pregnant or will become pregnant during treatment

All subjects are free to withdraw from the study at any time without stating a reason or suffering from any disadvantage. In addition

Mandibular Repositioning

Feature (MRF)

Protocol Number: MRF-002

Group Assignment

Schedule of Study Visits

Screening

Subjects must be screened before enrollment in the study. Screening procedures by the investigator will include the following:

- 1. Perform a dental history exam
- 2. Review inclusion and exclusion criteria (Eligibility criteria)
- 3. Inform subject and obtain written informed consent

Initial Visit

Initial visit procedures and tasks will include the following:

Mandibular Repositioning

Protocol Number: MRF-002

8. Case Report Form: Enrollment Form

Aligner Delivery Visit

- 1. Deliver Aligners: Give the prescribed aligners to the subject and instruct them on how to wear the aligners with MRF features
- 2. Subject (QoL) Form: To be filled out by the subject.

3 Months After Start of Mandibular Advancement

4.1.3 End Study

The End of Study occurs when a subject has completed all study related visits. When all subjects have completed the study, a report will be written concluding the findings from the study.

4.2 Number of Subjects/ Assignment to Treatment Groups

This study will enroll up to 165 patients. It is recommended that each site enroll a minimum of 10 subjects, to facilitate pooling of the data. It is recommended that each site recruits a minimum of 1 subject to have the occlusal feature set and a minimum of 1 subject

4.3 Sites

This study will be conducted at multiple sites in North America.

14 ALIGN CONFIDENTIAL

Protocol Number: MRF-002

4.4 Subject Withdrawal

Subjects have the right to withdraw from the study at any time for any reason. The Investigator or Sponsor may withdraw the subject at any time for any reason. If any subject withdraws or is withdrawn from the study, any non-study records that were taken while the subject was enrolled in the study will not be shared with the study Sponsor and there will be no requirement to continue treatment according to this protocol. Withdrawal from the study will not result in any penalties and will not preclude or interfere with the investigator's treatment of the subject outside of the study. Additional subjects may be enrolled to substitute for any withdrawn subject until the study target enrollment is reached.

5. DATA COLLECTION PLAN

The schedule of all study activities and procedures is provided

No additional invasive or other burdensome interventions in comparison to the standard care will be performed.

6. DATA ANALYSIS

Data will be analysed by the Sponsor's statisticians or an identified consultant. The data will be analysed using standard univariate and bivariate techniques.

Significance will be demonstrated to a 80%

confidence level.

6.1 Primary endpoint analysis:

The primary objective of the study will be to demonstrate that Invisalign with MRF is not inferior to existing functional appliances to treat up to full cusp Class II malocclusions in growing teenagers. The objective will be met if Invisalign aligners with MRF correct Class II malocclusions at a rate that is not inferior to previously reported repositioning rates. This will be achieved if the median rate of correction using Invisalign with MRF at the end of the mandible repositioning is non-inferior to published rates of movement (0.42 mm/mo.

The secondary endpoints measured by

comparing the length of treatment

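### The visible plan specifies no adjustment of the secondary length-of-treatment comparison for the millimetres of correction needed, so in this non-randomised study it may be confounded by case severity

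*Combined protocol and SAP*

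**What the plan says.** - **Method.** Section 6 (Data Analysis) describes the analysis of all data in one sentence: "The data will be analysed using standard univariate and bivariate techniques". It is tied to no single endpoint.
- **Endpoint.** Section 6.1 lists a secondary endpoint measured by "comparing the length of treatment". The words on either side are missing from the public text, so the comparator cannot be seen.
- **Design.** Section 4.1: "This study is a prospective, non-randomized Investigational Device Exemption study". The text under Group Assignment in section 4.1.2 is also missing.
- **Range of severity.** Under the inclusion criteria in section 4.1.2 a subject "must require at least 3mm of correction as measured by first molar relationship". The objective reaches "up to full cusp Class II malocclusions in growing teenagers", with no millimetre value for that upper end.
- **Primary endpoint.** The median rate of correction is to be "non-inferior to published rates of movement (0.42 mm/mo", that is, distance per unit time.
- **Confidence level.** At the end of section 3.1: "All statistical comparisons will be conducted to an 80% confidence level".

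No visible section names a covariate, a stratification factor, a matching step or a multivariable model.

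**The concern.** Section 4.1.2 defines the end of repositioning as the point at which Class II has become Class I. The time to reach it therefore depends on two things: how far the molars have to move and how fast they move. Only the second is device performance.

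A comparison of length between groups already uses two variables, length and group. Taking account of millimetres needed brings in a third, which is beyond bivariate methods as normally understood. Without randomisation, nothing in the design balances severity between groups or between this sample and a published one. A difference in length could appear, or a real one be hidden, because one set of subjects started further from Class I. The result could then be read as a property of the device when it is partly case mix. Section 4.1 says that data from the correction may be used for publication or regulatory purposes, so the reading matters.

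**Working it through.** The plan gives no figure for this comparison, and the sample size in section 6.2 is missing from the public text, so there is nothing to reproduce. The check is of the mechanism and its size.

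**Inputs from the documents:** benchmark rate 0.42 mm/month (section 6.1); minimum correction 3 mm (section 4.1.2); enrolment up to 165 (section 4.2); 80% confidence level (section 3.1).

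**Step 1: months per millimetre.** For the repositioning phase, T = D / R, with D the millimetres needed and R the rate. At R = 0.42, one millimetre takes 1 / 0.42 = 2.38 months.

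| D (mm) | D / 0.42 (months) |
|---|---|
| 3 | 7.1 |
| 4 | 9.5 |
| 5 | 11.9 |
| 6 | 14.3 |
| 7 | 16.7 |
| 8 | 19.0 |

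Values above 3 mm are illustrative, because full cusp is not given in millimetres. A 1 mm difference in mean severity shifts unadjusted mean length by about 2.4 months with no difference between devices.

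**Step 2: the share of variation in length due to severity.** Since log T = log D − log R, and taking D and R as independent,

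share = var(log D) / [var(log D) + var(log R)].

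Assumptions, none of them in the documents: D uniform from 3 mm to the stated upper value; R lognormal with coefficient of variation CV, so that var(log R) = ln(1 + CV²).

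| Upper D | CV 0.10 | CV 0.20 | CV 0.30 | CV 0.50 |
|---|---|---|---|---|
| 5 mm | 68% | 35% | 20% | 9% |
| 6 mm | 80% | 50% | 31% | 15% |
| 7 mm | 85% | 60% | 40% | 21% |
| 8 mm | 89% | 66% | 47% | 26% |

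The share runs from 9% to 89%. It exceeds half only if the CV of rate is below about 0.15 to 0.28, depending on the upper limit. The documents give no SD for rate or for millimetres needed, so the share cannot be fixed.

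**Step 3: how small an imbalance could matter (illustration).** Assume 165 subjects in two equal groups, an SD of length of 3 to 5 months, and a two-sided 80% level (z = 1.28); sidedness is not stated for this comparison. The threshold for declaring a difference is 1.28 × SD × √(2 / 82.5), or about 0.6 to 1.0 months. Dividing by 2.38 gives a mean imbalance of about 0.25 to 0.42 mm. Against a fixed published figure the threshold is 1.28 × SD / √165, about 0.3 to 0.5 months, or 0.13 to 0.21 mm. Unequal groups would raise the between-group threshold.

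**The case against.** The strongest reply is that the endpoint sentence is cut on both sides. The comparator, any matching, and what length covers are all out of sight, and removed text may not be counted against the plan. This stands as a limit: an adjustment or a matched comparator in the removed text cannot be excluded. The point therefore rests on the visible study-wide sentence alone.

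A reader might infer that section 6 makes adjustment impossible. The documents do not support that. The sentence is a general description and excludes nothing. If the comparator is a published figure, group is not a variable in the data, and regressing length on millimetres needed is itself bivariate. Dividing length by millimetres is also open to the plan, but it gives the reciprocal of the primary rate and so adds little. The gap is sharpest for a between-group comparison, where length, group and millimetres make three variables.

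Two further replies stand. First, T = D / R describes only the repositioning phase. Section 4.1 has subjects continue with aligners afterwards, and if length includes that phase, each millimetre still adds time but severity's share of the variation is smaller. Second, the primary endpoint already divides by distance, so a severity-scaled measure of performance will be reported beside the length result.

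**Conclusion.** The point holds as a gap in the visible plan for a secondary endpoint. Length of treatment is to be compared in a non-randomised study, subjects differ in the correction they need, and no visible text takes account of that difference. The comparison may be confounded by severity, at about 2.4 months per millimetre of mean imbalance in the repositioning phase. That figure rests only on the plan's 0.42 mm/month.

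A reader might go further and infer that the comparison mostly reflects severity. The documents do not support this: the share is anywhere from 9% to 89% under the assumptions shown. Nor do they show that an imbalance exists; they show only that nothing visible guards against one. No gain in precision from adjustment is claimed either, since that would need a correlation between millimetres and length that the documents do not give.

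The change is worth making because it costs almost nothing and fixes the covariate before results are seen. It does not bear on the primary conclusion.

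**What to change.** In section 6, state the comparator for length of treatment and which phases length covers, and add wording such as:

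- Any between-group comparison of length of treatment will use linear regression (on log length if skewed) with baseline first-molar discrepancy in mm as a covariate. Unadjusted figures will be given as descriptive.
- Where the comparator is a published figure, the model-predicted length at the published sample's mean baseline discrepancy will be compared with it, provided that mean is reported and was measured comparably. Otherwise the comparison will be labelled descriptive.

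Age may be added as a covariate but is not needed for this point.

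**Cost.** One degree of freedom and a change of wording, with no extra visits or subjects. The discrepancy has to be assessed to apply the 3 mm rule, and a rate in mm/month also needs millimetre data. Because the initial-visit procedures are in removed text, the sponsor should confirm that the baseline value itself is recorded and not only whether the threshold was met. The published-comparator option also needs a published mean that the documents do not give, which is why it has a descriptive fallback.
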